# A randomized controlled Trial to Compare the Histomorphometric and Clinical Outcomes of Soft Tissue Augmentation at the Time of Lateral Ridge Augmentation Procedures.

### Study Protocol

### 1. Objectives/Specific Aims:

The purpose of this investigator-initiated study is to evaluate the effect of soft tissue autogenous vs allogenic grafts on the soft tissue quantity and quality at the time of Guided Bone Regeneration (GBR) in preparation for endosseous implant placement.

Autogenous Connective Tissue Grafting (CTG) and Acellular Dermal Matrix (ADM) soft tissue grafts are mainly used to alter the quality and quantity of soft tissue.

a) Core objectives of this study are to:

1) To evaluate the quality of soft tissue regenerated with the use of the two available soft tissue grafts via histological analysis.

2) To evaluate whether CTG or ADM influences the outcomes of Guided Bone Regeneration (GBR) procedures.

3) To quantify the soft tissue augmentation achieved by the two available soft tissue grafts by direct clinical measurements after the healing

b) Outcomes will be measured by an evaluation of the following:

- 1) The quality of soft tissue regenerated with the use of the two available soft tissue graft via histological analysis (attachment to bone and keratinization)
- 2) Keratinized tissue width (in mm) measured clinically with a periodontal probe from the implant collar to the mucogingival junction.
- 3) Vertical thickness of soft tissue (in mm) measured clinically with periodontal probe around the implant collar from soft tissue surface to bone contact.
- 4) Volumetric change of soft tissue dimensions around the implant collar evaluated by superimposition of pre- and post-grafting digital intra-oral scan.

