Various surgical techniques have been used to obtain adequate amounts of keratinized tissue around dental implants, including the gingival autograft, apically positioned flap (APF), coronally positioned palatal sliding flap, and acellular dermal matrix graft (ADM). Performing a free gingival graft (FGG) prior to im- plant surgery has been suggested when there is minimal keratinized tissue over the edentulous ridge and APF and FGG can be combined in shallow vestibules with minimal keratinized tissue. A recent systematic review demonstrated that the combination of apically positioned flap and free gingival graft (FGG) is the most successful approach to increase the width of keratinized tissue and deepen the vestibule. However, when comparing the use of epithelialized gingival grafts with free connective tissue grafts, their ability to promote keratinized tissue is similar.

These procedures are usually performed before implant placement or during the exposure of submerged implants, which can extend the healing period and result in patients suffering from pain and discomfort through several surgical stages. In addition, these can be time-consuming procedures in cases that already have good primary implant stability and do not need hard-tissue augmentation.

To our knowledge, the influence of soft tissue augmentation at the time of ridge augmentation procedure has not been tested in socket grafting (ridge preservation) and ridge augmentation (deficient healed site) defects. This study aims at evaluating the effects of soft tissue augmentation using CTG or ADM on the clinical (amount) and histologic (% vital bone) outcomes at time of lateral ridge augmentation.

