Group 3: Control group (no soft tissue augmentation at time of lateral augmentation)

During bone augmentation procedure, just before suturing the flaps that were reflected, a CTG (Harvested from the patient's palate) or ADM (donor tissue that is FDA approved) will be sutured to the membrane that covered the bone graft.

**Visit 2:** The sutures will be removed after two weeks. Surgical sites (CTG, ADM or Control group) will be evaluated for healing status and postoperative instructions on resuming oral hygiene measures will be instructed to patients. Review medical history and assess for adverse events experience.

**Visit 3:** Six months post-ridge augmentation, For the research purposes a soft tissue biopsy will be taken at the center of the augmented site after elevating the flap using a 2 mm tissue punch. It is noteworthy that this soft tissue specimen would have been typically drilled away (automatically discarded in the suction system) with the initial implant site preparation drill if a biopsy were not planned (regular clinical setting). Hence, the biopsy procedure will not affect in any negative way the likelihood of implant placement. One Soft tissue biopsy per every participant in each group will be harvested from the site that was augmented and each tissue sample will be labelled a unique set of numbers and/or letters.

The soft tissue biopsy will be harvested and fixed in special solution overnight at 4°C. Fixed tissues will be dehydrated through an ethanol gradient, cleared in xylene, and embedded in paraffin. Embedded Tissues will be sagittal sectioned at 7mm thickness and mounted on Superfrost Plus slides (Fisher Scientific, Hampton, NH, USA). Serial sections of biopsy containing epithelia and connective tissue will then be cleared in xylene, rehydrated, and stained with hematoxylin and eosin (H&E) according to

standard protocol. The samples will be store to the laboratory located in the Institute of Oral Health Research at UAB School of Dentistry for the analysis of the tissue samples.

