#### 7. Data Analysis/Outcome measures

The null hypothesis is CTG and ADM materials will have the same soft tissue thickness and possible attached tissue (as demonstrated by histology) at time of implant placement. To reject the null hypothesis of equal means with a significance level (alpha) of 0.05 using a two-sided two-sample unequal-variance t-test, 22 patients in each group (total of 66) will reach 0.90 statistical power. Accounting for a 6-patient loss-to-follow up, 60 patients will be enrolled in the study.

Outcomes will be measured by an evaluation of the following:

- 1) the quality of soft tissue regenerated with the use of the two available soft tissue grafts via histological analysis (attachment to bone and keratinization)
- 2) Keratinized tissue width (in mm) measured clinically with a periodontal probe from the implant collar to the mucogingival junction.
- 3) Vertical thickness of soft tissue (in mm) measured clinically with a periodontal probe around the implant collar from soft tissue surface to bone contact.

4) Volumetric change of soft tissue dimensions around the implant collar evaluated by superimposition of pre- and post-grafting digital intra-oral scans

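### Outcome 4 is labelled soft tissue volume change, but the scans as described measure bone and soft tissue contour together in every arm

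*Combined protocol and SAP*

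**What the plan says.** Outcome 4 appears twice. Section 7 (Data Analysis/Outcome measures) gives it as "Volumetric change of soft tissue dimensions around the implant collar evaluated by superimposition of pre- and post-grafting digital intra-oral scans". Section 1 (Objectives/Specific Aims) repeats the definition, "evaluated by superimposition of pre- and post-grafting digital intra-oral scan", and adds nothing on timing, region or alignment.

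Section 3 describes the operation. All three groups have lateral ridge augmentation. In groups 1 and 2 the CTG or ADM "will be sutured to the membrane that covered the bone graft", just before the flaps are closed. Group 3 has the bone procedure without a soft tissue graft.

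Two places treat bone as a possible consequence of the soft tissue graft. Core objective 2 in section 1 is "To evaluate whether CTG or ADM influences the outcomes of Guided Bone Regeneration (GBR) procedures". The aim at the end of section 2 refers to "clinical (amount) and histologic (% vital bone) outcomes at time of lateral ridge augmentation".

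The only CBCT named is the one used in section 4 to establish ridge width for eligibility. None of the visits in section 3 lists an intra-oral scan.

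**The concern.** A surface scan cannot see the boundary between bone and soft tissue. If the first scan precedes the operation and the second follows it, everything added beneath the surface is in the difference: bone graft, soft tissue graft, and healing of the flap. The plan calls that whole quantity soft tissue.

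Two things are at stake. The first is description: each arm's mean change would be reported as soft tissue gain when part of it, and possibly most of it in controls, is bone. The second is comparison: if the soft tissue graft changes how much bone is gained, a difference between arms in outcome 4 could come from bone, from soft tissue or from both. An opposite bone difference could equally hide a real soft tissue effect.

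**Working it through.** **1. What the measurement contains.** For one patient and a fixed region, write C for the contour change between scans, B for the bone change and S for the soft tissue change. The scan gives only

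C = B + S.

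| Arm | Bone augmentation | Soft tissue graft | Content of C |
|---|---|---|---|
| CTG | yes | yes | B + S |
| ADM | yes | yes | B + S |
| Control | yes | no | B + S, where S is flap and healing change only |

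Separating S needs a measure of B over the same interval, or a scan taken between the two grafts. Section 3 describes neither. The Visit 3 specimen is a soft tissue biopsy and gives no bone volume.

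**2. Within-arm mean.** The mean of C equals mean B plus mean S. It equals mean S only if mean B is zero, which is contrary to the purpose of the augmentation. So the label is wrong for every arm whatever the between-arm result.

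**3. Between-arm contrast.** For arms 1 and 2,

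mean C1 − mean C2 = (mean S1 − mean S2) + (mean B1 − mean B2).

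The second bracket is the bias when the contrast is read as soft tissue. It is zero if bone gain is the same in both arms.

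**4. Whether the listed outcomes would reveal that bias.** Outcome 1 is histology of the soft tissue, outcome 2 is keratinized width, outcome 3 is probed thickness down to bone, and outcome 4 is the scan. None gives bone amount, so the second bracket would go unseen.

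**5. The plan's own figure.** Section 7 states 22 per group for 0.90 power at two-sided alpha 0.05, with no difference or SD, and does not tie it to outcome 4. It cannot be reproduced from its inputs; solving backwards gives a standardised difference of 1.00.

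**6. Illustration of size.** The documents give no SD and no bone effect, so the bone difference b, in SDs of the scan measurement, is assumed. The true soft tissue difference is set to 0.

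- Patients per arm: (60 − 6) / 3 = 18 with the stated losses; 60 / 3 = 20 with none.
- Test: one pairwise two-sided t-test, alpha 0.05, df = 2n − 2, noncentrality b × √(n/2). With n = 18 and b = 0.5 this is 0.5 × √9 = 1.5 on 34 df.

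| b (SD of scan measurement) | 18 per arm | 20 per arm | 22 per arm |
|---|---|---|---|
| 0 | 5% | 5% | 5% |
| 0.1 | 6% | 6% | 6% |
| 0.25 | 11% | 12% | 13% |
| 0.5 | 31% | 34% | 37% |
| 1.0 | 83% | 87% | 90% |

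The entries are the chance of a significant result that would be labelled soft tissue. If b is instead expressed in soft tissue SDs, with bone and soft tissue SDs equal and independent, values of 0.25, 0.5 and 1.0 at 18 per arm give 8%, 18% and 54%.

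**7. Timing and region.** The only follow-up contacts described are Visit 2 ("The sutures will be removed after two weeks") and Visit 3 ("Six months post-ridge augmentation, For the research purposes a soft tissue biopsy will be taken"). The scan is assigned to neither. The region is set by an implant collar, but section 5 places implants after the bone graft has healed. The collar is therefore absent from the first scan, and from both if the second precedes implant placement. No rule carries the region from one scan to the other.

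**The case against.** The strongest reply is randomisation. Every arm gets the same bone procedure, so if bone gain is equal, the contour difference between arms is the soft tissue difference. This stands as far as it goes: the contrast is a valid randomised comparison of total contour in any case, and its error rate as a soft tissue test stays at 5% when bone gain is equal. It does not rescue the within-arm values, and the plan cannot assume equal bone gain while asking in core objective 2 whether the grafts alter bone outcomes.

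Second, the percentages are ordinary t-test power at assumed effects and would be the same for any contaminant of any outcome. That is correct. A reader might infer that the trial faces a 31% or 83% false-positive rate; the documents contain nothing to support any particular bone difference, and they do not specify a pairwise test for outcome 4.

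Third, a reader might infer that the second scan could as well be taken at two weeks. The documents do not name a scan visit, but the context favours the healed stage: core objective 3 concerns augmentation after healing, and the section 7 null hypothesis refers to implant placement.

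Fourth, a reader might infer that only outcome 4 lacks a scheduled visit. Section 3 does not assign outcomes 2 and 3 to a visit either; the biopsy alone has one. Section 4 mentions required postoperative diagnostic evaluations without saying what they are, which does not supply a bone measurement.

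Finally, the consequence is limited: outcome 4 is the last of four, and the hypothesis and sample size are framed on thickness and histology.

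**Conclusion.** Outcome 4 is wrong as labelled. As described, it measures combined bone and soft tissue contour change in all three arms, and its within-arm values cannot be reported as soft tissue change. This rests on a surface scan recording only the outer contour, on the first scan preceding the operation, and on no bone subtraction being described.

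A reader might go further and infer that the between-arm comparison is biased. The documents do not support that. Bias in the soft tissue reading arises only if bone gain differs by arm, which the plan leaves open and has no listed outcome to check. Its size is unknown; the tabulated figures show how it would grow, not what to expect.

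Outcome 3 is unaffected, because probing from the soft tissue surface to bone excludes bone change. The point should be corrected, but it does not undermine the trial's other outcomes.

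**What to change.** In sections 1 and 7, rename outcome 4 *total ridge contour change (hard plus soft tissue)*, and state that soft-tissue-only conclusions are drawn from outcome 3.

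In the same edit:

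- state both scan time points in section 3, the same for all arms, with the second after healing;
- define the region on one registered scan and project it onto the other, so that it does not depend on a collar missing from the first.

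The renaming is wording only. The other two items need a schedule entry and a short written procedure; the scans are already implied by outcome 4, and no patients are added. No additional CBCT is needed under this correction.

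The downside is that the trial no longer claims a soft-tissue-only volume, and outcome 3 covers vertical thickness at the collar only.

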# 8. Confidentiality

Data will be stored in a password-protected study-specific computer database within the department of Periodontology. The computer is backed-up by UAB IT. Knowledge of passwords and access to the database will be strictly limited to study personnel who are working with the collected data.

# 9. Adverse Event Reporting

Participants will be interviewed and instructed to call if they experience any adverse events after study procedures. Such events will be recorded. In the event of a serious adverse event, the IRB will be notified per posted requirements and in full compliance with federal guidelines for research in human subjects.
